To evaluate between-treatment differences for the proportion of patients with new vertebral fractures at Month 12 relative to baseline.	Title: Incidence of new vertebral fractures Unit of measure: number and percentage of new vertebral fractures Description: See Section 6.4.1 Time frame: baseline, and 12 months	Section 9.5.1.4
To evaluate the between-treatment differences for change in vertebral morphometry at Month 12 relative to baseline.	Title: Change in vertebral morphometry Description: Quantitative morphometry will be performed by a central reader (see Section 6.4.1 ) Time frame: baseline, and 12 months	Section 9.5.1.5
To evaluate the between-treatment differences for change in pain using the Faces Pain Scale-Revised (FPS-R) at Months 3, 6, 9 and 12 relative to baseline.	Title: Change in pain scale Description: Children will select the face that best fits their pain ( Appendix 4 ) Time frame: baseline, 3, 6, 9 and 12 months	Section 9.5.1.7
To evaluate the between-treatment differences for change in 2nd metacarpal cortical width at Month 12 relative to baseline.	Title: Change in metacarpal cortical width Description: The X-ray Manual provides instructions on the technique. Skeletal bone age will be determined as described in the Imaging Charter Time frame: baseline and 12 months	Section 9.5.1.6
To measure urinary concentration of zoledronic acid at Month 12.	Title: Pharmacokinetics Unit of measure: ng/mL Description: urine will be collected overnight or for at least 4 waking hours from all patients able to provide specimens Time frame: 12 months	Section 9.5.3
The safety objective is to demonstrate that zoledronic acid is safe for the treatment of osteoporotic children treated with glucocorticoids through the monitoring of relevant clinical and laboratory safety parameters	Title: Safety: adverse events, laboratory evaluations and vital signs Description: adverse events will be collected from the first infusion (Visit 2), blood and urine samples, including renal monitoring will be collected (See Section 6.5 ). Also bone safety (change in LS-BMD) is monitored at months 6 and 12. Time frame: baseline through 12 months	Section 9.5.2

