
1 V1 lab results, including GFR should be available prior to V2
 
2 All randomized patients will have limited blood chemistry assessments, GFR & urinalysis performed at Visit 3 (10 days after Visit 2) and Visit 6 (10 days after Visit 5). An optional repeat at V2 is included, if the time between screening and V2 is close to 4 weeks.
 
3 Test to be performed for females with childbearing potential only. Serum test for central laboratory at screening and final visits, local urine test prior to infusion at Visits 2 and 5 – if positive, infusion should not be started.
 
4 Screening DXA and X-rays should be performed at Visit 1 to ensure the central imaging laboratory can provide status on patient eligibility; these assessments should be performed early in the screening process.
 
5 Ionized Ca measured pre-dose (local lab) only before the first infusion, if below normal range, treat and repeat test before study drug infusion, if visit needs to be re-scheduled inform the monitor.
 
6 Lumbar spine, total body and [REDACTED]
 
7 Lateral thoracolumbar spine and posteroanterior (PA) left hand/wrist (for bone-age assessment and cortical bone thickness)
 
8 Including an oral examination for exposed bone. At screening visit the PI will perform an oral exam and , if needed, will refer the patient to a dentist
 
9 For exclusion purposes if increase between Visits 1 and 2 greater than 0.5 mg/dL (44.2 µmol/L).
 
10 Pain is assessed using Faces Pain Scale-Revised (FPS-R)
 
11 An AP (anteroposterior) spine X-ray will be employed at screening, in order to identify fractures that may not be readily visualized on the lateral spine because of rotation/scoliosis/other
 
[12 Only sites where additional safeguards required: Supervised urine pregnancy test]
 
 	
 
15 SAEs only to be collected from signing informed consent
 
16 Pulse rate and blood pressure only
 
17 Urine collection for PK: either an overnight sample, or collected over at least 4-hours during the day, for details, see Lab Manual
 
18 Screening visit can be on different days to permit scheduling of all investigations during the 28-day screening period
 
T = Telephone visit, S = Source documentation, D = Database, GC = Glucocorticoid, TD = study treatment discontinuation, PSW = Premature patient withdrawal
																	

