## **6.6 Other assessments**

### 6.6.3 Pharmacokinetics

Further details on sample collection, numbering, processing and shipment can be found in the Laboratory Manual

Urine will be collected into a polypropylene container during at least a 4-hour sampling period at Visit 8 (Month 12). The first morning sample may be used if the time of the previous night's bladder voiding is recorded, otherwise it should be discarded (see Laboratory Manual for further details).

All samples will be given a unique sample number. The actual sample collection date and time will be entered on the PK urine collection page of the eCRF.

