#### Pharmacokinetics parameters

Aet1-t2 will be calculated as  $A_{et1-t2} = \text{urine volume (t1-t2)} \times \text{urine concentration}$ .

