### 9.5.3 Pharmacokinetics

[figure not shown]
ZOL446 urine concentration data will be listed by treatment, subject, and visit/sampling time point.

[figure not shown]
Descriptive summary statistics will be provided by treatment and visit/sampling time point, including the frequency (n, %) of concentrations below the LLOQ and reported as zero.

Summary statistics will include mean (arithmetic and geometric), SD, CV (arithmetic and geometric), median, minimum and maximum. Concentrations below LLOQ will be treated as zero in summary statistics. A geometric mean will not be reported if the dataset includes zero values.

Pharmacokinetic parameters will be calculated as described in [Section 6.6.3](#) and will be listed by treatment and subject. Descriptive summary statistics will include mean (arithmetic and geometric), SD, and CV (arithmetic and geometric), median, minimum and maximum.

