Descriptive summary statistics will be provided by treatment for urine concentration of zoledronic acid at Month 12, including mean (arithmetic and geometric), standard deviation (arithmetic and geometric), coefficient of variation (CV) (arithmetic and geometric), median, first quartile (Q1), third quartile (Q3), minimum and maximum. Furthermore, frequency (n, %) of zoledronic acid concentrations below the Lower Limit of Quantification (LLOQ) will be displayed, which is defined as 10 ng/mL. Concentrations below LLOQ will be treated as zero in summary statistics. A geometric mean will not be reported if the dataset includes zero values. The same summary statistics will also be provided for PK parameter Aet1-t2 at Month 12, which is calculated as urine volume (t1-t2) x urine concentration. A listing of concentrations of zoledronic acid at Month 12 will also be provided.

Safety evaluation

All safety analyses will be performed on the Safety Population. The assessment of safety will include adverse events, laboratory tests (hematology, blood chemistry and urine values), vital signs, and tanner staging score. Patient listings will be provided for all safety data.

Adverse events

An adverse event (AE) is any untoward medical occurrence in a subject or clinical investigation subject after providing written informed consent for participation in the study until the end of study visit. Treatment-emergent adverse events will be defined as adverse events that were absent prior to the first infusion and occurred after the first infusion during the study or that were present prior to the first infusion and occurred at increased severity after the first infusion during the study. Summarization will be based on treatment-emergent adverse events. Adverse events will be coded using the Medical dictionary for regulatory activities (MedDRA). The number and percentage of patients who report adverse events will

be summarized by treatment according to the primary system organ class and preferred term. If a patient reports more than one adverse event within the same primary system organ class (preferred term), the patient will be counted only once with the greatest severity at the system organ class (preferred term) level. Serious adverse events and selected adverse events will be presented by treatment group code. Listing of these events will be provided.

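### The summary of urinary zoledronic acid amount (Ae) pools collections of different lengths with no time term, so for quantifiable samples it partly reflects how long urine was collected.

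*SAP*

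**What the plan says.** **Collection.** Urine for PK is collected once, at Visit 8 (Month 12). Protocol Table 2-1 says "urine will be collected overnight or for at least 4 waking hours from all patients able to provide specimens". Footnote 17 of Table 6-1 says "either an overnight sample, or collected over at least 4-hours during the day" and refers to the Laboratory Manual for details. Protocol Section 6.6.3 also sets a 4-hour minimum. It allows the first morning sample only if the time of the previous night's voiding was recorded. None of these places gives a maximum or a common interval.

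**Recorded times.** Section 6.6.3 states: "The actual sample collection date and time will be entered on the PK urine collection page of the eCRF".

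**Derived parameter.** Section 6.6.3 defines one PK parameter, Aet1-t2, as urine volume over the interval times urine concentration. The SAP repeats the definition: "PK parameter Aet1-t2 at Month 12, which is calculated as urine volume (t1-t2) x urine concentration".

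**Summary.** The SAP states: "The same summary statistics will also be provided for PK parameter Aet1-t2 at Month 12". Those statistics are the arithmetic and geometric mean, SD and CV, the median, quartiles, minimum and maximum, by treatment. Protocol Section 9.5.3 plans a similar summary and a listing of PK parameters by subject. Concentrations below the LLOQ of 10 ng/mL count as zero in both documents.

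**Objective.** Secondary objective 8 is urinary concentration at Month 12, in ng/mL (protocol Section 2.2 and Table 2-1).

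**The concern.** Ae over t1 to t2 is a total for one child's own interval. If two children excrete the drug at the same rate and one collects for twice as long, that child's Ae is twice as large. A pooled mean is then an average of rate times duration, and a pooled CV contains the spread of durations as well as the spread of excretion.

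Neither document defines an excretion rate, a common interval, a split by overnight or daytime collection, or any other standardisation for length. Neither commits to listing the collection duration beside Ae, so a reader of the planned output could not make the correction.

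What is at stake is the meaning of the Ae table, which describes drug still being excreted about six months after the second infusion. No test or efficacy result depends on it.

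**Working it through.** The documents give no figure for Ae, so there is none to reproduce. The check shows how far Ae moves when only the collection length changes.

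**Inputs from the documents**
- Ae = volume × concentration (protocol Section 6.6.3; SAP, Pharmacokinetic (PK) evaluations).
- Shortest daytime collection: 4 h (protocol Table 2-1, Table 6-1 footnote 17, Section 6.6.3).
- LLOQ 10 ng/mL, with lower values set to zero (protocol Sections 6.6.3 and 9.5.3; SAP).

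**Assumptions, not in the documents**
- Overnight collections last L = 8 to 12 h.
- Daytime collections last exactly 4 h.
- The excretion rate R is constant and equal in all children. R = 100 ng/h is used for display; ratios and CVs do not depend on it.
- A share p of children collect overnight: 50%, with a range of 25 to 75%.

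**Step 1: effect on one child.** Ae = R × T, where T = t2 - t1.

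| T (h) | Ae (ng) | Ratio to 4 h | Ae/T (ng/h) |
|---|---|---|---|
| 4 | 400 | 1.0 | 100 |
| 8 | 800 | 2.0 | 100 |
| 10 | 1000 | 2.5 | 100 |
| 12 | 1200 | 3.0 | 100 |

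**Step 2: effect on the pooled CV.** For a mix of 4 h and L h:

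CV = √(p(1 - p)) × (L - 4) / (pL + 4(1 - p))

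At p = 50% this is 2/6 = 33% for L = 8, 3/7 = 43% for L = 10, and 4/8 = 50% for L = 12.

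| Share overnight | L = 8 h | L = 10 h | L = 12 h |
|---|---|---|---|
| 25% | 35% | 47% | 58% |
| 50% | 33% | 43% | 50% |
| 75% | 25% | 31% | 35% |

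The range is 25 to 58%, although every child excretes at the same rate.

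**Step 3: effect on the pooled mean.** With 4 h and 10 h collections at 100 ng/h, the mean is 0.25 × 1000 + 0.75 × 400 = 550 ng when a quarter collect overnight. It is 0.75 × 1000 + 0.25 × 400 = 850 ng when three quarters do.

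**Step 4: a less extreme pattern.** If lengths were spread evenly from 4 to 10 h instead of falling at two points, the CV from length alone would be (6/√12)/7 = 25%.

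**Step 5: samples below the LLOQ.** Concentration is set to zero, so Ae = volume × 0 = 0 for any T. Steps 1 to 4 apply to quantifiable samples only.

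**Step 6: after dividing by time.** Ae/T is 100 ng/h in every row of step 1. The ratio becomes 1.0 and the CV from collection length becomes 0%.

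**The case against.** A reader might infer that secondary objective 8 cannot be interpreted as planned. The documents do not support that. The objective is a concentration in ng/mL, which is not multiplied by collection length, and Ae is an added descriptive parameter. Concentration does depend on how dilute the urine is, but that is a separate matter and dividing Ae by time would not change it.

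A reader might also infer that the times needed are certainly in the database. Section 6.6.3 puts the sample collection date and time in the eCRF, but does not expressly say that both start and stop are captured. The previous voiding time is a condition for using a first morning sample, and the text does not say that it is entered in the eCRF. No start time is mentioned for daytime collections. The Laboratory Manual may settle this and may narrow the collection window, but it is not available here. Capture of the times therefore has to be confirmed.

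Three further objections stand in part:
- The size rests on assumptions. Longer daytime collections would shrink the contrast, and the excretion rate may differ between day and night.
- The share of samples below the LLOQ is not given. If it is large, the mix of zero and non-zero values could affect the pooled CV more than collection length does.
- A rate does not make children fully comparable. Dosing is by weight (0.05 mg/kg, maximum 5 mg). At assumed weights of 15 and 60 kg the doses are 0.75 and 3.0 mg, a 4-fold difference that remains in ng/h.

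It is also true that nothing is tested on Ae, and that a rate could be derived later if the times exist. These points limit the importance of the issue. None of them puts a time term into the planned Ae summary.

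**Conclusion.** The point holds for the Ae summary and is minor. In both documents Ae has no time term, collection length may vary by design, and the values are pooled by treatment. For quantifiable samples the reported mean and CV will partly describe how long urine was collected.

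Under the stated assumptions (constant rate, 4 h by day, 8 to 12 h overnight), Ae differs 2.0 to 3.0-fold at equal excretion. Length alone gives a CV of 33 to 50% at an even split, and 25 to 58% for overnight shares of 25 to 75%. These figures are illustrations, not predictions. The existence of the effect needs only that lengths differ among children with quantifiable samples. The concentration endpoint and all efficacy analyses are untouched.

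**What to change.** In the SAP's Pharmacokinetic (PK) evaluations:
1. Confirm that start and stop times are both captured in the eCRF for overnight and for daytime collections.
2. Keep Ae, and list each child's collection duration and type beside it.
3. Add the excretion rate Ae/(t2 - t1) in ng/h, with the same descriptive statistics, overall and split by overnight or daytime collection.
4. State how many samples are below the LLOQ in each split, because their Ae and rate are zero whatever the duration.

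If both times are captured, the cost is one derived variable, a few listing columns and one more summary. Children with a missing start or stop time drop out of the rate summary, and their number should be reported. Variation from the weight-based dose remains, so the rate should not be presented as fully standardised.

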### **3 Investigational plan**

#### **3.1 Study design**

This will be an international, multicenter, randomized, double-blind, placebo controlled efficacy and safety study recruiting osteoporotic children and adolescents receiving glucocorticoid therapy within the 12 months preceding screening who manifest a LS-BMD Z-score of -0.5 or worse plus evidence of low impact/fragility fracture.

At the baseline visit (Visit 2), patients whose eligibility is confirmed will be randomized to one of two treatment groups. Patients may be hospitalized at the discretion of the investigator for observation following the first study drug infusion. Ionized calcium will be assessed before the first study drug infusion only. Patients will receive the second study drug infusion at the Month 6 visit. Safety and efficacy will be assessed at 6 and 12 months, with additional telephone visits to assess adverse events [REDACTED] and concomitant medication at 3 and 9 months. Renal safety utilizing the Schwartz calculation for GFR will be assessed at screening, and 10 days after the i.v. infusion of study drug 6 and 12 months.

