## Risks

### Known risks of zoledronic acid

Since this protocol was first written in 2008, there have been more publications on the potential use of bisphosphonates in children with kidney diseases including nephrotic syndrome (Gruppen et al 2013, Sbrocchi et al 2011).

ZOL is concentrated and excreted via the kidney and, like other bisphosphonates, has the potential to produce renal injury. Thus, care should be taken when administering the compound to patients with renal insufficiency. Although case reports have been published in adult medicine regarding the nephrotoxicity of ZOL with an incidence of acute kidney injury (AKI) between 9% and 13%, bisphosphonate-induced, AKI in children remains undocumented (Patzner 2008).

- In this protocol, patients are excluded if they have an estimated GFR  $< 60$  mL/min/1.73 m^2 or a rising serum creatinine increase greater than 0.5 mg/dL (44.2 μmol/L) between Visit 1 and Visit 2. Patients who have nephrotic syndrome with osteoporosis, who do not meet these exclusion criteria, have been stable for 3 months prior to enrollment, and meet the remaining eligibility criteria can be considered for this study.

Post-infusion acute phase reactions are more common after the first infusion and can include pyrexia, muscle and joint pain.

- To reduce the risk of these reactions, children will be instructed to eat and drink as usual, NSAIDs or acetaminophen (paracetamol) will be prescribed and an anti-emetic may be provided to reduce the risk of symptomatic hypocalcemia if the child develops nausea or starts to vomit. Further calcium supplements will be provided for up to 10 days at the time

of infusion and parent/guardian instructions provided on the signs to watch for as well as an emergency number, if needed.

Hypersensitivity reactions including anaphylactic reaction, anaphylactic shock, angioedema, bronchospasm and urticaria are listed in the IB. Therefore, children with a previous known hypersensitivity are excluded. Should a child develop a hypersensitivity reaction, it must be reported as an adverse event.

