**Table 5-1 Recommended minimum daily dietary allowances (Ross 2011)**

Age	Vitamin D	Calcium
≥ 5 years to ≤ 8 years	600 IU	1000 mg
≥ 9 years to ≤ 17 years	600 IU	1300 mg

All patients should take at least 600 IU vitamin D daily from Visit 1 until the final Visit through diet and/or supplementation.

Elemental calcium, at least 1000 mg for 5-8 years of age or at least 1300 mg for 9-17 years of age, daily will be taken beginning at Visit 1 and during the total duration of the trial, through diet and/or supplementation. Calcium carbonate is the preferred form of calcium supplementation. If calcium carbonate is not well tolerated, another form of oral calcium would be acceptable.

Any vitamin D and calcium supplements will be recorded on the Concomitant medications/Significant non-drug therapies (e)CRF.

In addition, transient hypocalcemia has been reported especially following the first infusion and it can cause symptoms in rare cases. To prevent the development of symptomatic hypocalcemia, the parent or guardian of each child will receive an information sheet and all patients will receive calcium supplementation at the doses recommended in [Table 5-1](#) starting from the day of infusion and for a minimum of 5 days after each infusion (for sites where this calcium supplementation usually starts prior to the infusion, the total treatment period is approximately 10 days in total) ([Hogler et al 2004](#)).

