#### **5.5.7.1 Treatment of study drug related adverse events:**

As with other bisphosphonates, zoledronic acid has been associated with post-dose symptoms that may include fever, nausea, myalgia, arthralgia and bone pain, with onset occurring within the first 72 hours after the infusion. Typically these symptoms occur with the first infusion of bisphosphonate. The symptoms are usually mild to moderate and rarely severe. These symptoms may be adequately managed, at the discretion of the investigator, with non-steroidal anti-inflammatory agents (e.g. acetaminophen/paracetamol or ibuprofen) and/or anti-emetics by local treatment standards and according to approved local labeling. Based on data from controlled trials, treatment with non-steroidal anti-inflammatory agents will reduce the incidence of these symptoms by approximately 50%. In managing these symptoms it is important to encourage adequate hydration and food intake.

All dosages prescribed and dispensed to the patient and all dose changes during the study must be recorded on the concomitant medications/significant non-drug therapies CRF after start of study treatment.

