Adverse event tables will be sorted alphabetically by system organ class and then according to decreasing frequency of preferred term in the zoledronic acid group. If only system organ classes or preferred terms are presented, these will be sorted according to the decreasing frequency in the zoledronic acid group.

The following sets of adverse events will be summarized:

- All adverse events (by primary system organ class and preferred term)
 - Adverse events suspected to be related to study drug (by primary system organ class and preferred term)
 - Adverse events that occurred after first infusion and before second infusion (by primary system organ class and preferred term)
 - Most frequent adverse events (at least 5% in any group) (by primary system organ class and preferred term)
 - All adverse events (by primary system organ class, preferred term and maximum severity)
 - All adverse events (by underlying disease group, primary system organ class and preferred term)
 - Adverse events that result in death (by primary system organ class and preferred term)
 - Serious adverse events (by primary system organ class and preferred term)
 - Adverse events causing permanent discontinuation of study drug (by primary system organ class and preferred term)
 - Adverse events associated with a change in renal function (by preferred term). Time to first adverse event associated with a change in renal function will be presented separately.
- [REDACTED]
- Hypocalaemia adverse events (by preferred term). Time to first hypocalaemia occurrence based on AE and central lab calcium will be presented separately.

Incidence of risk as defined in the case retrieval strategy, during the study period, will be summarized by treatment group, and MedDRA levels. Relative risk of zoledronic acid group

vs. placebo will be presented along with corresponding 95% confidence intervals using the Mantel-Haenszel test.

Missing date convention

Partial AE start dates: If an AE start date is completely missing, then no imputation is implemented. AEs with completely missing start dates will be treated as treatment emergent. If the year of an AE start date is missing but the month is available, then the date will be imputed as the start date of the first study drug infusion + 1.

If the year is not missing and the month is missing, then date will be imputed as follows:

- If the AE year is less than the year the study drug infusion was administered, then July 1st of the year will be used.

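### No readable adverse-event table uses the 72-hour post-infusion window that the protocol describes, or isolates the second infusion; short-window tables per infusion would be a cheap improvement

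*SAP*

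**What the plan says.** **Timing of the known reactions.** Protocol Section 5.5.7.1 names fever, nausea and muscle, joint and bone pain as post-dose symptoms, "with onset occurring within the first 72 hours after the infusion", and adds: "Typically these symptoms occur with the first infusion of bisphosphonate". Section 3.6 agrees: "Post-infusion acute phase reactions are more common after the first infusion and can include pyrexia, muscle and joint pain". On calcium, Section 5.1.2 notes that "transient hypocalcemia has been reported especially following the first infusion".

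**Counting windows.** The SAP, under Adverse events, opens its list with "All adverse events (by primary system organ class and preferred term", which has no time limit. One set is bounded in time: "Adverse events that occurred after first infusion and before second infusion (by primary system organ class and preferred term". Protocol Section 3.1 fixes its length: "Patients will receive the second study drug infusion at the Month 6 visit". The relative risk is also computed over the full study: "Incidence of risk as defined in the case retrieval strategy, during the study period, will be summarized by treatment group, and MedDRA levels". Time to first event is planned for renal and hypocalcaemia events and runs to last contact.

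**Counting rule.** Within a system organ class or preferred term, each patient is counted once. Treatment emergence is judged only against the state before the first infusion.

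**Redaction.** One bullet in the list, between the renal and the hypocalcaemia sets, is blacked out.

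**The concern.** The protocol puts these reactions in the first three days after an infusion. The readable tables count them over six or twelve months. Eligible diseases include systemic-onset juvenile arthritis, lupus, dermatomyositis and inflammatory bowel disease, in which fever and joint or muscle pain could plausibly arise in either arm over such periods. Any such background enters both arms and shrinks the ratio between them.

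The second infusion is a separate difficulty. Subtracting the between-infusion table from the overall table does not give the incidence after the second infusion. A child with fever after both infusions appears once overall and once between infusions, and so vanishes in the subtraction. The readable tables therefore cannot show whether a reaction recurs.

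**Working it through.** **1. Arm size.** Protocol Section 9.8 and the SAP assume a difference of 0.63, SD 0.93, two-sided alpha 0.05 and 85% power. The t-test power is 84.9% at 40 per arm and 85.8% at 41 per arm, which reproduces 82 evaluable patients. Then 82/(1 - 0.10) = 91.1, rounded up to 92, or 46 per arm. This figure is not disputed; it only supplies n for the illustration, taking all randomized patients as treated.

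**2. Window lengths.** Three days is 3/180 = 1.7% of the between-infusion period and 3/365 = 0.8% of the year.

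**3. Model.** Let b12 be the 12-month background risk of the symptom in both arms and r the risk of a drug-caused reaction soon after the first infusion. Neither is in the documents; both are assumed to lie between 10% and 40%. With a constant background hazard:

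- placebo risk over t days: b(t) = 1 - (1 - b12)^(t/365)
- zoledronic acid risk: 1 - (1 - b(t))(1 - r)
- risk difference: r(1 - b(t))

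**4. Worked case, r = 20%, b12 = 30%.**

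| Window | Zoledronic acid | Placebo | Risk difference | Risk ratio | Fisher power |
|---|---|---|---|---|---|
| 3 days | 20.2% | 0.3% | 0.20 | 69 | 0.90 |
| 180 days | 32.9% | 16.1% | 0.17 | 2.04 | 0.37 |
| 365 days | 44.0% | 30.0% | 0.14 | 1.47 | 0.21 |

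For 365 days: 1 - 0.70 × 0.80 = 0.44, and 0.20 × 0.70 = 0.14. Power is for the exact two-sided Fisher test at 0.05 with 46 per arm.

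**5. Range of power.**

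| r | b12 | 3 days | 180 days | 365 days |
|---|---|---|---|---|
| 10% | 10% | 0.31 | 0.22 | 0.15 |
| 10% | 40% | 0.30 | 0.09 | 0.06 |
| 20% | 10% | 0.91 | 0.68 | 0.50 |
| 20% | 20% | 0.91 | 0.49 | 0.32 |
| 20% | 40% | 0.89 | 0.29 | 0.15 |
| 40% | 10% | 1.00 | 0.99 | 0.97 |
| 40% | 40% | 1.00 | 0.83 | 0.55 |

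A longer window lowers the risk difference by the factor 1 - b(t) and the risk ratio far more. The direction is the same in every scenario run; the size is not.

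**6. Date rules.** Under the SAP's Missing date convention for adverse events, three kinds of partial start date become the day after the first infusion: month known but year missing; year equal to the infusion year but month missing; and only the day missing in the infusion month. In the last case the rule takes the later of the first of the month and treatment start + 1, which is always treatment start + 1. Such events would fall inside a 3-day window after the first infusion whatever their true date. In later months a missing day becomes the first of the month, which bears no relation to the second infusion.

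**The case against.** **The redacted set may already be this table.** It stands among the special-interest sets. The readable subsections that follow describe only renal and hypocalcaemia events, but details of a redacted set could be redacted too. A reader might infer that the plan has no post-infusion analysis; the documents do not support that.

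**Other planned outputs remove some background.** There are sets for events suspected to be drug-related and for events by underlying disease, plus listings, and the treatment-emergent rule drops symptoms already present at the same severity. These help, but none is a time window. The causality set rests on judgement, the disease split divides about 92 patients further, and the emergence rule can also drop a true reaction in a child who already had equally severe joint pain.

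**The size is assumed.** This stands in full. Section 3.6 says antipyretic or anti-inflammatory medication will be prescribed, and Section 5.5.7.1 puts the reduction in symptoms at about 50%, so a low excess is plausible. No test is planned for the general adverse-event tables, so power here only shows how visible a signal would be.

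**Laboratory hypocalcaemia is already separable.** Because the time-to-event analysis mixes samples taken 10 days and 6 months after an infusion, a reader might infer that the early calcium results are lost. They are not: the SAP subsections on hypocalcaemia and on laboratory parameters summarize low calcium by visit, so Visits 3 and 6 stand apart from Visits 5 and 8. What remains is that hypocalcaemia reported as an adverse event has no post-infusion window.

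**Conclusion.** A cheap improvement rather than an error in the plan. The protocol places the symptoms within 72 hours, while every readable table and the relative risk use about 180 days or the whole study, and none isolates the second infusion. The cost depends on rates that the documents do not give. With an assumed 20% excess it is substantial on the ratio scale and in power, but at 30% background the risk difference falls only from 0.20 to 0.14. With a large excess and low background there is almost no loss, and with a 10% excess a short window is itself weak. It would therefore go too far to infer that the planned tables will hide a real reaction. The failure to show recurrence after the second infusion needs no assumed rate; it follows from counting each patient once. Both parts hold only if the redacted set does not already cover the matter.

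**What to change.** Unless the redacted set already does so, add to the SAP, by arm:

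- Adverse events with onset within 3 days of the first infusion and, separately, within 3 days of the second, by preferred term and as one group of the Section 5.5.7.1 symptoms, with exact 95% confidence intervals for the risk difference. The denominator is the patients who received that infusion. Define the window in calendar days, since Section 7.1 asks for start and end dates.
- Hypocalcaemia adverse events with onset within 10 days of each infusion.

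Base these tables on complete start dates. Show events with imputed dates only as a separate count or a sensitivity version. Keep the existing tables as the overall summary; the by-visit calcium tables need no change.

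The cost is SAP wording and a few descriptive tables with small counts. No new data are needed, and trial conduct does not change.
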